5.3.1 Epilepsy Protocol for rTMS at low frequencies in Epilepsy (short-term protocol)

Epilepsia partialis continua (EPC) can be considered the status epilepticus (SE) equivalent of focal onset seizure with retention of awareness. EPC may occur as a single episode, repetitive episodes, and it may be chronic progressive or non-progressive. The significance of this work is to address the efficacy of the short-term use of rTMS in the treatment of EPC patients. This study will employ a carefully planned low frequency rTMS protocol, with therapeutic sessions over a short period of time (3 to 5 days), with a possible extension phase protocol if initial study is successful.

Existing protocols that are related to this work [1-7] are listed in Table 3. These were reviewed in order to bring in synergy the strengths of each for carrying out safe and effective rTMS sessions. Accordingly, we propose a short term trial in patients with EPC, to test whether LF-rTMS can reduce/suppress the status epilepticus, and determine for how long such outcomes can last for each patient. The proposed protocol that will be followed in this study is described in Table 4 on the basis of the knowledge gained from these previous studies.

During each session EEG will be recorded. Goal recruitment will be 10 acute phase medically refractory participants, based on the following:

- At least 2 medications failed
- At least 24 hours of acute phase
- Family consent or available proxy (legal representative)

Equipment:

The MagVita TMS is CE approved for “treatment of Major Depressive Disorder. MagVenture’s rTMS system is effective and it is an alternative to medications.

Table 3: Existing Protocols.

Cited Literature	Frequency	Threshold	Stimuli	Schedule	Coil	Outcome-seizures	Position	Stimulation time
Gersner, et al. 2016 (1)	20Hz	80%MO	500/train	10 trains of 3s with 30s intertrain One time	8	Reduced epileptic spike frequency decreased seizures during stimulation	vertex	Single 5 min.

Repeated TMS at Low Frequencies to Reduce Seizure Occurrence

Liu A, et al. 2015 (3)	1Hz	70%MO		1 train	8	Reduced epileptic spike frequency and seizures	3D source	20 min.
Rotenberg, 2009 (4)	1Hz: 1800 sec.	100%MT	3 trains	3 trains		Seizures stopped	3D source	1800 sec
Graff Guerrero. 2004(5)	20Hz	50%MO	15 trains	15 trains of 2 sec		Seizures stopped	3D source	
Graff Guerrero. 2004(5)	20Hz	128%MT	15 trains	15 trains of 2 sec		Improved EEG	3D source	
Schrader LMKL, 2005 (6)	0.5 Hz	100%MT	16 trains of 900 sec	2 trains per session, biweekly, for 4 weeks)		decreased seizures	3D source	
Misawa S, 2005 , (7)	0.5 Hz	90%MT	1 train of 200 sec	1 train		Seizures stopped	3D source	

MT: Motor threshold, MSO: Maximum stimulator output

Table 4: Suggested short-Term Protocol for this Study: (Stimulation time: minutes)

Frequency	Threshold	Stimuli	Schedule	Coil	Position	Study Design
1Hz	100%MO		Up to 5 days/	8	3D Source Localization or vertex	Open-label

5.3.2 Limitations and Alternative Approaches

While TMS is a safe, painless, technically easy procedure, because the orientation of the magnetic field of stimulation needs to be perpendicular to the electrical field of stimulation, TMS may not always generate a response. In such a case, the benefit of the stimulation technique may be limited. The abductor pollicis brevis (APB) is a low voluntary recruitment threshold motor unit, easily activated in most individuals using TMS. However, should this fail to activate with maximal stimulation, another muscle of similar threshold can be substituted: either the first dorsal interosseous or the abductor digiti minimi. These muscles are all in the palm of the hand.

5.3.3 Emergency Response and Treatment Protocol in case of Seizure

A neurologist ([name]) will be on the premises at all times during the rTMS treatment. In the immediate vicinity of the TMS machine where the patient is laying down on a comfortable chair similar to the ergonomic dental chair, no harmful objects will be present. In case a patient suffers the occurrence of a seizure during an rTMS session, the following steps are undertaken:

Repeated TMS at Low Frequencies to Reduce Seizure Occurrence

- Code rescue will be initiated for the management of acute seizure for patient safety according to hospital's protocols and as below.
- Diastat AcuDial (diazepam rectal gel) will be kept at the chair side in case any seizures are provoked. DIASTAT is a gel formulation of diazepam intended for rectal administration in the management of selected, refractory patients with epilepsy, on stable regimens of AEDs, who require intermittent use of diazepam to control bouts of increased seizure activity for patients 2 years and older.
- If a seizure occurs, testing (TMS) will be postponed at least 1 hour, or until baseline function returns.
- Patient will be placed on their left side in the recovery position to promote airway and prevent aspiration.
- Harmful objects will be moved out of the way, head will be protected.
- Patient will not be restrained. Objects will not be placed in the mouth. Adequate ventilation will be ensured.
- Respiratory changes such as skin color increase/decrease in respiratory rate and noisy or congested breathing will be monitored. If the patient is not breathing, rescue breathing will be started immediate medical attention will be followed. Suction apparatus, clean gloves and pillows will be available for immediate use.

<http://www.epilepsy.com/get-help/staying-safe> and <http://www.epilepsy.com/get-help/managing-your-epilepsy>

<http://www.emergencycareforyou.org/EmergencyManual/WhatToDoInMedicalEmergency/Default.aspx?id=268>

<http://www.webmd.com/epilepsy/epilepsy-seizure-what-to-do-in-an-emergency>

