-----------	-----------	---------	----------	------	----------	-------

Repeated TMS at Low Frequencies to Reduce Seizure Occurrence

						Design
1Hz	120%MT	800	5 days/week for 2 weeks 1/week for 1 month 1/month for 11 months	8	3D Source Localization, vertex, and bipolar frontal	double-blinded, sham-controlled
1Hz	120%MT	800	5 days/week for 2 weeks 1/week for 1 month 1/month for 11 months	8	coil will be placed with an angle of 45 degrees with respect to the scalp without direct contact	double-blinded, sham-controlled

Using a single-blinded, sham-controlled design, we will screen patient's age 2 to 80 years with focal and generalized intractable epilepsy. Baseline data will include a detailed seizure diary over 4 weeks, psychometric testing/neuropsychology evaluation, and 20-minute EEG recordings. Each patient will then begin treatment with 14 minute sessions of 1 Hz rTMS or sham rTMS, 120%MT, and 800 stimuli on the position of the calculated 3D source using EEG, MRI, and digitized electrode locations. The protocol will be divided in 3 groups (Groups 1, 2 and 3) as follows:

- Groups 1, 2, and 3: LF-rTMS for 2 weeks (5 days per week for total of 10 days).
- Group 1: protocol total duration: 1 year: LF-rTMS 1 session/week for 1 month (4 days), and LF-rTMS 1 session/month for 11 months
- Group 2: protocol total duration: 1 year: LF-rTMS 1 session/month for 12 months
- Group 3 (placebo protocol, total duration: 1 year): LF-rTMS 1 session/week for 1 month (4 days); and LF-rTMS 1 session/month.

During each session EEG will be recorded. Also, we would update number of events and frequency data from ongoing seizure diary. Psychometric testing will be performed at the beginning of study, 3 months, and at the end of the study. Thus, each patient will have rTMS testing, psychometrics, and EEG recordings.

Goal recruitment will be 90 medically refractory participants, with 30 participants for each of the three groups, based on the following:

- At least 3 seizures in one month
- No status epilepticus for 1 year
- No change in medication for 1 month

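### The in-session seizure rule joins its two recovery conditions with *or*, treats a repeat seizure like a first, and no written rule holds the next session after status epilepticus between sessions

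*Combined protocol and SAP*

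**What the plan says.** The steps in Section 5.3.3 apply "In case a patient suffers the occurrence of a seizure during an rTMS session". Most of them are acute care: code rescue for the "management of acute seizure for patient safety according to hospital's protocols and as below", positioning, airway care, and rectal diazepam that "will be kept at the chair side in case any seizures are provoked". A neurologist "will be on the premises at all times during the rTMS treatment". One sentence governs further stimulation: "If a seizure occurs, testing (TMS) will be postponed at least 1 hour, or until baseline function returns". It does not distinguish a first seizure from a later one.

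The long-term schedule in Table 2 (Section 5.3) is "5 days/week for 2 weeks 1/week for 1 month 1/month for 11 months". Entry to that phase requires "No status epilepticus for 1 year" and at least 3 seizures in a month. Seizure data are gathered throughout: "Also, we would update number of events and frequency data from ongoing seizure diary". Section 5.2.1 repeats the motor threshold at every treatment visit and puts motor mapping at 15 to 20 minutes. Section VII describes withdrawal as the participant's choice. No other supplied section says when stimulation is delayed, reviewed or ended after a seizure.

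**The concern.** A postponement rule should make the operator wait for the later of two things: a fixed interval and clinical recovery. With *or*, the literal instruction is met by the earlier of them. Section 5.1 assigns the procedures of Sections 5.1 to 5.3 to university research personnel, so the wording has to be safe for someone following it as written.

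Two gaps sit beside it. A patient who has a seizure at one session and another at a later one gets the same postponement each time, with no step that prompts a wider look. And status epilepticus within the past year keeps a patient out of the long-term phase, yet an episode between two sessions holds nothing in writing. What is at stake is re-stimulating an individual at 120% of motor threshold without a recorded decision that it is still appropriate.

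**Working it through.** There is no figure in the plan to reproduce on this point. The check has three parts.

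**1. The wording.** Let R be the time to return of baseline function.

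| Reading | Earliest restart | R = 20 min | R = 3 h |
|---|---|---|---|
| Literal *or* | earlier of 1 h and R | 20 min | 1 h, not recovered |
| *and* | later of 1 h and R | 1 h | 3 h |

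The R values are illustrations. The literal reading fails in both directions.

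**2. What a second-seizure review would address.** Planned sessions (Section 5.3):
- Group 1: 10 + 4 + 11 = 25.
- Group 2: 10 + 12 = 22.
- Group 3: 25, taking the 11 months in the sham row of Table 2, because the text leaves the number of monthly sessions open.
- Total: 30 × (25 + 22 + 25) = 2,160.

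The documents give no in-session risk for 1 Hz; the 1% in Section 5.5.1 is attached to high frequencies. So the per-session risk p is assumed over a range, with sessions independent. For n sessions:
- P(second seizure) = 1 − (1−p)^n − np(1−p)^(n−1).
- Mean sessions after the second seizure = Σ over t of (n−t)(t−1)p²(1−p)^(t−2).

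Example: n = 25, p = 0.01 gives 1 − 0.778 − 0.196 = 0.026.

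| p | n = 25: second seizure | Later sessions | n = 22: second seizure | Later sessions |
|---|---|---|---|---|
| 1% | 2.6% | 0.21 | 2.0% | 0.14 |
| 5% | 36% | 3.4 | 30% | 2.4 |
| 10% | 73% | 8.4 | 66% | 6.4 |
| 20% | 97% | 15.2 | 95% | 12.3 |

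The later sessions are averaged over all patients with that p, including those with no second seizure.

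**3. What the second-seizure hold would cost by chance.** Suppose seizures fall at random and stimulation has no effect. The mean number of in-session seizures per patient is sessions × (rate/30) × (minutes/1440). At 3 per 30 days and 14 minutes this is 25 × 0.1 × 14/1440 = 0.0243, or 0.0214 for 22 sessions. The expected number held is 60 × P(≥2 | 25 sessions) + 30 × P(≥2 | 22 sessions), using Poisson counts or a negative binomial with variance twice the mean. Adding 15 to 20 minutes of mapping makes each visit 29 to 34 minutes.

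| Seizures per 30 days | 14 min, Poisson | 14 min, variance 2× | 29–34 min, Poisson | 29–34 min, variance 2× |
|---|---|---|---|---|
| 3 | 0.02 | 0.4 | 0.10–0.14 | 0.9–1.0 |
| 10 | 0.26 | 1.4 | 1.1–1.4 | 3.0–3.6 |
| 30 | 2.1 | 4.5 | 7.7–10.0 | 10–12 |

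All entries are patients out of 90. The same chance model shows that the rule is likely to be used. At the minimum entry rate, 2,160 × 0.1 × 14/1440 = 2.1 seizures are expected inside stimulation windows, an 88% chance of at least one. A hold after the *first* in-session seizure would catch about 2.1, 6.7 and 18.7 of 90 on the 14-minute Poisson count, which is why the second is the better trigger.

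**The case against.** The natural reading of the sentence may be a one-hour floor, extended if recovery is slower. That is plausible, and it makes the first part a drafting fault rather than evidence of unsafe intent. It does not remove the need to correct a safety instruction whose literal meaning differs.

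Section 5.3.3 is also a bedside emergency procedure. A reader might infer that the plan authorises indefinite re-stimulation without medical oversight. The documents do not support that. Each in-session seizure triggers code rescue, a neurologist is on the premises, and participants may withdraw. The hospital protocols, the consent pages and the safety guidelines cited in Section II were not available for this review, so a hold rule may exist there. What stands is narrower: the supplied text states no such rule.

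A reader might take 36% to 97% as the expected frequency of repeat in-session seizures. It is not. Those figures assume risks of 5% to 20% per session, which have no source in the documents, and nothing says how many patients would be that susceptible. By coincidence alone, the risk in 14 minutes is about 0.1% per session at 3 seizures per 30 days and 1.0% at 30.

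A reader might also fault the plan for having no rule on sustained seizure worsening. Diary counts are updated without a stated action, but that is unspecified detail, not a stated rule that is wrong. A worsening threshold would be a clinical trade-off, and the change proposed here does not depend on it.

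**Conclusion.** The point holds as a correction to one stated safety rule, with a short addition. Two parts rest on the text alone: either condition suffices as written, and a repeat in-session seizure is handled like a first. The third, that nothing holds the next session after status epilepticus between sessions, is limited to the supplied documents.

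The benefit cannot be sized at trial level, because it depends on an unknown per-session risk. It is negligible at 1% and substantial for a susceptible patient at 5% or more. The chance cost is small at the minimum entry rate, at most about one patient in 90 under the least favourable of the assumptions shown. It reaches about 12 of 90 only if patients average 30 seizures per 30 days, counts are overdispersed and full mapping recurs at every visit, which Section 5.2.1 does not make clear. The correction is worth making because its cost is low, not because a large harm has been shown.

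**What to change.** In Section 5.3.3:
- Replace *or* with *and*, so that both the 1-hour minimum and recovery of baseline function are required. For patients in the short-term epilepsia partialis continua protocol, define baseline as the state before the session, since ongoing seizures are the condition being treated.
- Add that in the long-term phase the next session is withheld until the on-site neurologist documents a review, without knowledge of group assignment, after (i) any status epilepticus, within or between sessions, or (ii) a second in-session seizure in the same patient.
- State whether in-session includes motor threshold determination and mapping, since that drives the number of chance holds.

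This adds a review, not a cap on repeats; continuing or stopping remains a clinical decision. It takes one changed word and a few sentences. The neurologist is already present and the diary and session records already exist, so no visits, patients, staff or committee are added. The price is an occasional delayed session, at the frequencies tabulated for trigger (ii). Trigger (i) was not costed, because the documents give no rate of status epilepticus.

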5.4 Multimodal Imaging

This TMS based protocol for epilepsy relies on multimodal imaging to benefit from (1) structural MRI for MRI-guided TMS motor threshold mapping and for situating in context the 3D source of seizure onsets; and (2) EEG for determining the 3D source exploiting the presence, positioning and singular nature of the interictal spike waveforms.

5.4.1 Magnetic Resonance Imaging -MRI

All patients that will undergo TMS brain stimulation would have had both magnetic resonance imaging (MRI) recording done at any of our collaborating hospitals (Miami Children's Hospital, Baptist Hospital or other) as it concerns this study. Since TMS is an MRI-guided machine, its use in conjunction with an MRI of a patient, it becomes possible to perform pinpointed navigated mapping of the language and motor areas of the brain. And when a 3D source is determined using interictal spikes of the EEG, such a source is also rendered in the context of the 3D brain of the patient.

5.4.3 Electroencephalography recordings - EEG

Repeated TMS at Low Frequencies to Reduce Seizure Occurrence

EEG recordings will be performed using the XLTEK EEG (Electroencephalograph) system. EEG signals will also be collected before and after some selected rTMS sessions, so that more comprehensive subject-specific connectivity maps could be obtained [54-57]. This is performed in order to assess the connectivity maps as a function of the determined position of the 3D source.

This system will be used to record the brain's spontaneous electrical activity and evoked responses non-invasively from the scalp. XLTEK EEG is a robust whole-head EEG system that can be used to record EEG activity so as to determine the 3D source of seizures on the basis of interictal spikes, or subsequent to this first step. Some of the research themes that will be investigated include (1) EEG activity analysis on the basis of the cortical and sub-cortical stimulation using repetitive pulse TMS (rTMS); (2) Study the functional connectivity between areas and the changes that occur in the brain before and after stimulating motor and language areas, respectively; (3) assess TMS-induced modulation of brain rhythms with respect to rest state.

Also EEG recordings in some cases may be performed using the Nexstim eXimia EEG system, designed specifically to be fully compatibility with the TMS machine, and is another major component that can be purchased alongside the TMS machine, which we did. *It is important to note that with the new TMS technology, an EEG module is fully integrated, and unlike the inherent noise in the integration of EEG and fMRI, both EEG and TMS signals are fully compatible as the TMS does not affect the EEG signal.* Consequently, EEG signals will also be collected during brain mapping, so that more comprehensive subject-specific connectivity maps could be obtained [54-57]. This is performed in order to assess the connectivity maps as a function of the determined position of the 3D source.

5.5. Risks Associated with the Recording Modalities

5.5.1 Risks of TMS

TMS often causes minor short-term side effects. These side effects are generally mild and typically improve after the first week or two of treatment. They can include:

- Headache.
- Scalp discomfort at the site of stimulation.
- Tingling, spasms or twitching of facial muscles.
- Lightheadedness.
- Discomfort from noise during treatment
- Mild and brief discomfort of the skin on the scalp from the Velcro strap or the EEG electrodes.

Uncommon side effects include:

- Mild and brief headaches or neck aches from the TMS stimulation. Serious side effects are rare. They can include:
- Seizure occurring during TMS stimulation at high frequencies. This has only been known to happen in 1% of children and adults with epilepsy, and in less than 1% of children and adults without epilepsy.

Repeated TMS at Low Frequencies to Reduce Seizure Occurrence

- Mania, particularly in people with bipolar disorder.
- Hearing loss due to inadequate ear protection during treatment.

5.5.3 Risks of EEG recording

There are no known risks for this standard noninvasive scalp EEG recordings, except for slight discomfort due to the placement of some of the electrodes that may be too tight on the scalp.

5.5.3 Minimizing Risks, Harms, and/or Discomforts

In order to reduce discomfort due to use of EEG electrodes, 'comfort rings' are used. As for rTMS stimulation, a mechanical arm with several degrees of freedom is designed to hold the TMS coil to eliminate any potential for pressure on the head of the subject, something that could happen if the coil were handheld by the clinician.

Previous studies have demonstrated that motor threshold mapping in normal subjects is not associated with provoking seizures [58].

VI. DATA TO BE COLLECTED AND DATA ANALYSIS PROCEDURES

Patients will be given a questionnaire to fill out their demographic and health information. Original medical records may be requested and stored by primary neurologist.

For each patient, the following types of data will be collected:

- A 3D MRI volume: This high resolution volumetric imaging data will be collected so that the final results could be displayed in concordance with the regions that were found to be active according to the task applied (motor or speech).
- Scalp EEG s in order to extract time and frequency domain parameters to assess the reaction of the brain to magnetic stimulation using different intensities and frequencies. The lateralization index will be calculated to define the dominant cerebral hemisphere for the language task.
- DICOM stimulation maps for motor threshold mapping.
- EMG data obtained from 1-6 EMG electrodes used for monitoring different muscle groups.

The data will be collected and stored for each patient undergoing the study. All the data will be de-identified by converting into alphanumeric values. The encoded values will be stored in password-protected servers accessible only to research personnel (FIU/Baptist) with authorization throughout data collection and analysis.

All identifiers will be removed from the data once they are transferred off the TMS computer and gathered into a pooling database, where each case will have a unique consecutive identification number. This information will be annotated in a separated document kept in the office of the PI ([name]).

Repeated TMS at Low Frequencies to Reduce Seizure Occurrence

Statistical analysis will be conducted using SPSS 14.0 software. The baseline seizure frequency and seizure frequency change after treatment will be computed from average weekly seizure frequencies before and after rTMS treatment for each patient. A patient data will be categorized into two treatment groups: rTMS treated and placebo groups.

VII. DESCRIPTION OF WRITTEN CHILD/ADULT CONSENT PROCESS

At a potential subject's visit to the physician's office or hospital, the investigator(s) will provide a comprehensive explanation of the purpose, procedures, possible risks/benefits of the study, and participant responsibilities, and discuss the fact that his/her participation is voluntary, that he/she may withdraw from the study at any time, and that the decision not to participate or to withdraw will not affect his/her regular medical care. Potential participants or their surrogates will be given ample opportunity to ask questions and to consider their decision. If the subject or the surrogate agree to participate, then a signed and dated written informed consent will be obtained.

A copy of the consent form will be given to the participant or the surrogate, and another copy will be placed in the subject's medical record. The informed consent form will be obtained by the investigators listed to perform informed consent procedures.

VIII. EXTENSION PHASE

If the results from this study demonstrate significant medical improvement, patients will be offered an extension phase where they could continue receiving the same parameters of stimulation for one to two additional years at no expense

REFERENCES

- [1] M. Kobayashi and A. Pascual-Leone, "Transcranial magnetic stimulation in neurology," *Lancet Neurology*, vol. 2, pp. 145-156, Mar 2003.
- [2] M. Hallett, "Transcranial magnetic stimulation and the human brain," *Nature*, vol. 406, pp. 147-150, Jul 13 2000.
- [3] P. M. Rossini and S. Rossi, "Transcranial magnetic stimulation: diagnostic, therapeutic, and research potential," *Neurology*, vol. 68, pp. 484-8, Feb 13 2007.
- [4] H. R. Siebner, G. Hartwigsen, T. Kassuba, and J. C. Rothwell, "How does transcranial magnetic stimulation modify neuronal activity in the brain? Implications for studies of cognition," *Cortex*, vol. 45, pp. 1035-1042, Oct 2009.

Repeated TMS at Low Frequencies to Reduce Seizure Occurrence

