The hypothesis is that low frequency brain stimulation focused on and around the seizure onset zone will reduce the occurrence of seizures over time. We base this hypothesis on clinical trials and reports on the treatment of seizures reported in the literature. It has been shown that high frequency rTMS, although beneficial in the treatment of patients with depression, can actually cause seizures [28], while low-frequency rTMS has the opposite effect in that it can actually inhibit the occurrence of such seizures. Modulating brain activity is shown to depend on the selection of the frequency used during stimulation [29, 30]. Therefore, and on the basis of this knowledge, we will restrict the brain stimulation process to a low frequency range between 0.5 and 1 Hz rTMS in people with focal and generalized epilepsy, while taking into consideration all the safety guidelines, ethical issues, and required precautions from prior research in the use of TMS technology [31, 32, 33].

The significance of this work is to address the efficacy of the long-term use of rTMS in the treatment of refractory epilepsy patients. Additionally, the integration of multimodal imaging where TMS, MRI, and EEG could provide data not available through DCS or fMRI alone, which in turn can only augment our understanding of brain mapping and brain dynamics. This study will employ a carefully planned low frequency rTMS protocol, with therapeutic sessions over a one-year time frame, with a possible extension phase protocol if initial study is successful.

III. RESEARCH OBJECTIVES

1. To reduce/suppress the number of seizures in patients with medically intractable epilepsy (partial and generalized) with the use of long-term LF-rTMS. Stimulation will be applied with determined seizure onset zone by inverse solutions and 3D software algorithms of analysis of electroencephalographic data. This objective is based on promising rTMS studies that reported reductions in seizure frequency. The primary continuous outcome measures for this aim will be seizure frequency, EEG epileptiform discharge frequency, seizure severity scale, and psychometric testing.
2. Statistical analysis will be conducted using ANOVA and secondary outcome measures will analyze the number of patients whose seizure frequency decreases by at least 50% (e.g., the “responder” threshold used in studies of anticonvulsant efficacy).

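### The seizure-frequency ANOVA names no baseline covariate and leaves 'change' and 'after' undefined, so the 4-week baseline diary may be used inefficiently

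*Combined protocol and SAP*

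**What the plan says.** Section III, item 1 lists four primary measures, seizure frequency first: "The primary continuous outcome measures for this aim will be seizure frequency, EEG epileptiform discharge frequency, seizure severity scale, and psychometric testing". Item 2 is the only place where a test is named: "Statistical analysis will be conducted using ANOVA and secondary outcome measures will analyze the number of patients whose seizure frequency decreases by at least 50" per cent.

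Section VI is the only text on how seizure frequency is derived: "The baseline seizure frequency and seizure frequency change after treatment will be computed from average weekly seizure frequencies before and after rTMS treatment". It then sorts patients into rTMS and placebo. It names SPSS but no test.

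Section 5.3 supplies the data. "Baseline data will include a detailed seizure diary over 4 weeks", and during the sessions "we would update number of events and frequency data from ongoing seizure diary". Recruitment requires "At least 3 seizures in one month", with no upper limit. There are 30 patients in each of three groups, so two active groups pooled against placebo is 60 v 30. All groups start with ten daily sessions over two weeks. The schedules then differ. For one active group the plan reads "Group 1: protocol total duration: 1 year: LF-rTMS 1 session/week for 1 month (4 days), and LF-rTMS 1 session/month for 11 months". The other active group goes straight to monthly sessions for the year, while the placebo group also has the weekly month.

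No section names a baseline covariate, a transformation or a count model.

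**The concern.** A change score subtracts the whole of a noisy 4-week baseline from follow-up, whatever the correlation between the two. ANCOVA estimates how much of the baseline to remove and, under random allocation, is at least as precise in large samples. With an entry minimum and no ceiling, seizure rates are likely to be skewed, so an absolute change would be dominated by the patients with most seizures.

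Two analysts could also follow Section VI faithfully and run different tests: absolute or percent change, over different diary weeks. The window matters because sessions continue to the end of the year, and Group 2 lacks the month of weekly sessions that Groups 1 and 3 have. At stake is how much the planned 90 patients can show, and whether the result can be interpreted without a choice made after the data are seen.

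**Working it through.** **The plan's own figure.** The target of 90 cannot be reproduced, because no alpha, power, effect size or standard deviation is given.

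**Inputs from the documents.** 60 v 30 patients; 4-week baseline; at least 3 seizures in a month; one-year protocol.

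**Inputs assumed.** Median 8 seizures per 4 weeks; between-patient log-SD 0.6-1.2 (this gives each range below); independent period log-SD 0.3 in baseline and follow-up; 30% reduction; 48-week follow-up window; two-sided 0.05; complete diaries.

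**Model.** Patient rates are lognormal. The baseline count B is Poisson over 4 weeks and the follow-up count F is Poisson over w weeks, with rate ratio 0.7 in the active arm. The tests are:
- absolute change: two-group ANOVA on F/w - B/4;
- percent change: the same on (F/w - B/4)/(B/4);
- raw ANCOVA: F/w on arm and B/4;
- log ANCOVA: log((F + 0.5)/w) on arm and log(B/4).

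**Case 1: entry rule applied to the baseline diary (B of at least 3).**

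| Setting | Absolute | Percent | Raw ANCOVA | Log ANCOVA |
|---|---|---|---|---|
| Base | 47-67% | 78-80% | 65-86% | 84-89% |
| 4-week window | 44-58% | 62-66% | 59-73% | 66-69% |
| Period log-SD 0.5 | 23-37% | 47-49% | 36-57% | 54-66% |
| 50% reduction | 81-97% | 100% | 98-100% | 100% |
| Gamma rates | 52-68% | 76-79% | 68-86% | 80-86% |
| Fixed fall of 0.6 seizures a week | 14-46% | 59-74% | 16-56% | 79-86% |

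In the base case the covariate alone gains 17-19 points over absolute change. Log ANCOVA gains 22-36, the remainder coming from the scale. Over percent change, log ANCOVA gains 4-11 points. Raw ANCOVA runs from 7 points better than percent change to 15 worse. Adding baseline to the percent-change model gains about 1-7 points. A 46-week window (52 - 2 - 4, counting only weeks when all groups are on monthly sessions) gives nearly the same: 47-66 / 78-80 / 64-85 / 84-88%.

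**Case 2: entry rule refers to an earlier month.** Baseline counts can then be very low or zero. With zero-baseline patients dropped for percent change and 0.5 added to baseline for the log model, power is 47-63 / 58-65 / 65-86 / 83-89%. Percent change trails log ANCOVA by about 20-30 points, and it is undefined for at least one patient in roughly half to three quarters of simulated trials (52-74%).

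**A check without skew.** In an additive normal model with baseline/follow-up correlation rho, the variance of the change-score estimate over that of ANCOVA is 2/(1 + rho). Where ANCOVA has 80% power, change-score power is Phi(2.80 x sqrt((1 + rho)/2) - 1.96). This is 0.62, 0.68, 0.73, 0.76 and 0.78 at rho 0.3, 0.5, 0.7, 0.8 and 0.9. The loss is therefore 2-7 points at rho of 0.7 or more.

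**Type I error.** With no effect, base case, all four tests rejected in 4.0-5.2% of trials.

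**The case against.** The strongest reply is that this is silence, not error. Section VI computes baseline frequency as a quantity of its own and may intend to use it, and in a plan this brief ANOVA may be a loose label. That stands: a reader might infer that the plan chooses to leave baseline out, and the text does not say so.

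Second, the gap between absolute change and log ANCOVA is not all due to the missing covariate. This also stands. Part of it is a move from arithmetic to geometric means. The covariate-only gain is model-dependent: about 2-10 points with a fixed weekly fall, and 2-7 in the normal model with high correlation.

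Third, the only numeric criterion in the plan, the 50% responder, is proportional. A reader might infer that the continuous change is percent too and that little is then lost. The documents do not define the continuous variable by that criterion. Nor do they say that the entry month is the diary month, on which the small loss depends. Even in the first case the loss is not always small: 59-74% against 79-86% with a fixed fall.

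Fourth, log ANCOVA has a different target and is partly a preference. That is fair, and it is a reason to choose the scale in advance.

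**Conclusion.** The gap in the text is certain: scale, window and use of baseline are all unspecified. If the ANOVA is run unadjusted on absolute change, the loss under the stated assumptions is about 17-19 points against the same analysis with baseline as covariate, and less in other models. If the change is percent, the loss against log ANCOVA is about 4-11 points or about 20-30 points, depending on which month the entry rule refers to. No rate, variance or effect behind these figures is in the documents, so the direction is firmer than the size.

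A reader might infer inflated false positives. The calculations do not show that: type I error is near 5%, provided allocation is random and response varies equally in both arms. The protocol describes sham control and blinding but not how patients are allocated, so random allocation is a condition here and not a finding. Without it, neither a change score nor ANCOVA would reliably remove baseline imbalance.

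This should be fixed. It concerns seizure frequency only, not the other three primary measures.

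**What to change.** In Section VI, state that follow-up weekly seizure rate (rTMS v placebo) is analysed by ANCOVA with the 4-week baseline rate as covariate. Preferably put both on the log scale, with a stated constant for zero counts in baseline and follow-up (for example 0.5 seizure), and report a rate ratio with 95% CI. If arithmetic means are the target, name raw-rate ANCOVA in advance instead. Also state:
- the diary weeks that count as after, for example those when all three groups are on monthly sessions, to the end of the year;
- that the rate is seizures per recorded diary week, and how short diaries are handled;
- whether the entry month is the baseline diary month;
- that change from baseline is descriptive, and whether it is absolute or percent.

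The cost is wording: both diaries are already planned, and the model is the named ANOVA with one covariate. There are two downsides. The log version compares geometric means. If response varies only in the active arm and arithmetic means are equal, it rejected in 6.6-7.2% of simulated trials at response log-SD 0.4 and in 36-38% at 0.8; the other three tests rejected in 2-4%. With a 4-week window the constant matters: power was 58-63% with 0.1, 66-69% with 0.5 and 69-70% with 1.
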